**Hospital Security Program for Engaging Communities with Firearm
Safe Storage Devices and Interventions: Data Collection Aim 2**

Study Protocol

January, 2024

Outline

1. Abstract
2. Overall objectives
3. Aims
 - 3.1 Primary outcome
 - 3.2 Secondary outcomes
4. Background
5. Study design
 - 5.1 Design
 - 5.2 Study duration
 - 5.3 Target population
 - 5.4 Accrual
 - 5.5 Key inclusion criteria
 - 5.6 Key exclusion criteria
6. Subject recruitment
7. Subject compensation
8. Study procedures
 - 8.1 Consent
 - 8.2 Procedures
9. Analysis plan
10. Human research protection
 - 10.1 Data confidentiality
 - 10.2 Subject confidentiality
 - 10.3 Subject privacy
 - 10.4 Data disclosure
 - 10.5 Data safety and monitoring
 - 10.6 Risk/benefit
 - 10.6.1 Potential study risks
 - 10.6.2 Potential study benefits
 - 10.6.3 Risk/benefit assessment

1. Abstract

To prevent workplace violence, in November 2021, Penn Medicine implemented the Evolv weapons detection system in Pennsylvania Hospital (1,2). For individuals who self-disclose they are carrying a weapon, or who are identified with weapon during screening, security guards offer the individual the option to leave with their weapon, or to place it in a safe, at the hospital, for storage. Security guards return the weapon when the patient or visitor is ready to leave. Beginning in July 2022 our team piloted a program in which security guards offer a cable lock and safety brochure when the gun owner returns to retrieve their firearm at the conclusion of their visit. To date, 47% of patients and visitors who stored their firearm with security have taken a cable lock when offered, resulting in over 300 firearm safety locks and brochures distributed to firearm owners. The Aims of this study are to: (1) Elucidate barriers and facilitators to implementing a hospital security screening firearm safety program through interviews with hospital security staff; (2) Design and pilot test a method for collecting data on storage device use among patients and visitors who accept firearm safety materials; (3) Conduct a pilot of distributing lockboxes and compare acceptance and usage rates to cable locks.

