5.5 Key inclusion criteria

Individuals who are visitors or patients at Pennsylvania Hospital, are identified through the Evolv system as carrying a firearm, and who accept firearm safety materials OR any patient or visitor interested in receiving a firearm storage device who self-selects into the study by scanning the QR code on the study poster. For eligibility of the follow-up survey, participants must have responded yes to taking a cable lock

in the initial brochure survey or yes to receiving a firearm storage device shipped to their address from the poster survey.

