8.2 Procedures

Study procedure. A unique QR code linking directly to the survey will be embedded into our firearm safety brochure and study poster available in the entry hall of PAH. Participants who scan positive for a firearm and are offered safety materials (inclusive of the brochure) will be informed that survey participation is optional, but that it is helpful to our efforts, and that participation will be compensated with a \$10 Amazon gift card for completing the initial survey and a \$20 Amazon gift card for completing the follow-up survey. Individuals who decline the device will also be eligible for the initial survey via the poster QR code. Gift cards will be distributed digitally via text in accordance with the participants consent to share their phone number. Only eligible participants will receive a text with a link to complete the optional follow-up survey.

Participants who self-select into the study via the study poster will be linked to the initial survey in Qualtrics with one re-worded question based on context. Individuals will receive \$10 Amazon gift card for completing the initial survey and a \$20 Amazon gift card for completing the follow-up survey. Only eligible participants will receive a text with a link to complete the optional follow-up survey.

Initial Survey via Brochure. Upon scanning the QR code on the brochure, an individual will be brought directly to the initial Qualtrics survey. The first question of the survey is a statement outlining that the individual's participation is voluntary and informed. The individual must select agree or disagree before proceeding with the survey. If the individual chooses to agree, they will then begin the initial survey. After completion of the survey, they will receive a text message with their Amazon giftcard information within 1-2 weeks. The text will read, "Hello, this is Penn Medicine. Thank you for participating in our survey. As an appreciation for your time, please see below for your gift card information: [INSERT GIFT CARD #]"

This initial survey will focus on the following elements. Survey language may be refined during the research process:

- 1.
2. To receive an Amazon gift card and participate in future follow-up surveys, please enter your phone number.
3. Most recent visit to Penn Medicine (mm/dd/yyyy)
4. Did you get a cable lock today?
 - a. Yes
 - b. No
5. [IF NO #3] What's the reason you didn't accept one?
 - a. Already have one
 - i. [LOGIC] How often do you use it?

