 1. Every time I store my device
 2. Almost every time I store my device
 3. Almost never when I store my device
 - ii. [LOGIC] What's your preference for storing your firearm? [text field]
 - b. Prefer different storage device
 - i. [LOGIC] Which of the following storage devices would you prefer?
 1. Lock box
 2. Trigger lock
 3. Gun safe
 4. Calmshell / "life jacket"
 5. Gun cabinet
 6. In-vehicle lock
 7. Other/key/PIN/biometric (please specify):
 - c. Don't want one
 - d. Not offered or not available
6. [IF YES #3] If you have accepted a device today, how likely are you to use it in the next week?
 - a. Extremely likely
 - b. Somewhat likely
 - c. Neither likely nor unlikely
 - d. Somewhat unlikely
 - e. Extremely unlikely
7. How do you usually store your firearm?
 - a. In a locked safe or gun cabinet
 - b. With a trigger lock or cable lock
 - c. Unlocked (not secured with a lock, in a locked container, or not stored in a locked cabinet)
 - d. Other (please specify)

Initial Survey via Poster. Upon scanning the QR code on the poster next to the distribution area, an individual will be brought directly to the initial Qualtrics survey. The first question of the survey is a statement outlining that the individual's participation is voluntary and informed. The individual must select agree or disagree before proceeding with the survey. If the individual chooses to agree, they will

then begin the initial survey. After completion of the survey, they will receive a text message with their Amazon giftcard information within 1-2 weeks. The text will read, "Hello, this is Penn Medicine. Thank you for participating in our survey. As an appreciation for your time, please see below for your gift card information: [INSERT GIFT CARD #]"

This initial survey will focus on the following elements. Survey language may be refined during the research process:

1. To receive an Amazon gift card and participate in future follow-up surveys, please enter your phone number.
2. Most recent visit to Penn Medicine (mm/dd/yyyy)
3. Are you interested in receiving a firearm storage device shipped to your address?
4. [IF NO #3] What's the reason you don't want one?
 - a. Already have one
 - i. [LOGIC] How often do you use it?
 1. Every time I store my device
 2. Almost every time I store my device
 3. Almost never when I store my device
 - ii. [LOGIC] What's your preference for storing your firearm? [text field]
 - b. Prefer different storage device

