 - i. [LOGIC] Which of the following storage devices would you prefer?
 1. Lock box
 2. Trigger lock
 3. Gun safe
 4. Calmshell / "life jacket"
 5. Gun cabinet
 6. In-vehicle lock
 7. Other/key/PIN/biometric (please specify):
 - c. Don't want to share my address
 - i. [LOGIC] Please select which of the following you'd be open to:
 1. Returning to Penn Medicine to pick up a free cable lock
 2. Receiving a free cable lock locally
 3. Other (please specify)
5. [IF YES #3] What is the best US shipping address for you?
 - a. [Text box fields for street, apt, city, zip, name]
6. How do you usually store your firearm?
 - a. In a locked safe or gun cabinet
 - b. With a trigger lock or cable lock
 - c. Unlocked (not secured with a lock, in a locked container, or not stored in a locked cabinet)
 - d. Other (please specify)
7. Once you receive your cable lock, how likely are you to use it in the next week?
 - a. Extremely likely

- b. Somewhat likely
- c. Neither likely nor unlikely
- d. Somewhat unlikely
- e. Extremely unlikely

Follow-up Survey: Participants who complete the initial survey and who agree to provide contact information will be contacted via text message 1 month after enrollment for a follow-up survey that adds questions about if and how participants have changed their storage behavior. The text language will read:

“Hello, this is Penn Medicine. Thank you for completing our initial survey. If you’re interested in taking the follow-up survey, please click the survey link below: [INSERT LINK]”

Participants will receive the second Amazon gift card incentive 1-2 weeks after completion of this survey. “Hello, this is Penn Medicine. Thank you for participating in our survey. As an appreciation for your time, please see below for your gift card information: [INSERT GIFT CARD #]”

The follow-up survey questions are subject to be amended based on the principal investigators’ discretion. Eligible participants from the initial survey, those who answered yes to accepting a cable lock, will be asked the following questions to understand if their behavior changed:

1. Since you’ve visited Penn Medicine, how have you stored your firearm? [option selection]
 - a. Participants select [a] in a locked safe or gun cabinet, b) with a trigger lock or cable lock, c) unlocked (not secured with a lock, in a locked container, or not stored in a locked cabinet), d) other (please specify) with an open comment box]

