2. Have you used the firearm storage device from Penn Medicine to secure your firearm? [Yes/No]
3. Have you made any other changes in your firearm storage? [write in]

Iterative Analysis and Refinement of Data Collection Methods: We will assess response rates every (1) week and tabulate responses on the acceptability of data collection methods. We will iteratively refine data collection methods over the course of 6 months to achieve the highest possible response rate. The participant data collected will be their phone number and/or their address for individuals completed the survey via the study poster. No identifying information or demographics will be collected to uphold anonymity. Cell phone number will be used to distribute the gift card via the Nudge Unit’s Google Voice account and re-contact with invitation to participate in the follow-up survey. Their address will only be used to ship the firearm storage device to individuals who self-enrolled in the study via the study posters.

9. Analysis plan

The primary outcome is survey response rate. This will be monitored via Qualtrics by looking at response volume by week. These responses will be compared to security department reports on the number of firearms identified/stored to allow us to calculate the proportion of eligible individuals who responded per week. The secondary outcome measures are: (1) firearm storage behavior among a) locked safe/gun cabinet, b) trigger lock or cable lock, c) unsecured, d) other (write in), (2) likelihood of using cable lock within the next week (extremely unlikely to extremely likely scale).

10. Human research protection

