This protocol is for Aim 2 and 3 of the study. The rationale for this aim is that traditional research methods for collecting data on firearm safe storage have not been optimized for use in a pragmatic setting to ensure acceptability and confidentiality. Our priority in firearm safety education and device distribution is to get the necessary information and supplies to those who need them. To achieve this, any data collection must be done in a low profile, confidential, and non-threatening way. This is particularly important not only because discussions of firearm ownership can be politically charged, but also because some community members may not be legally licensed to own or carry a firearm, and some may even be legally prohibited from doing so. The legal status of their ownership does not lessen their need for safety information and support—indeed, unlicensed firearm owners may have even fewer safety resources available for them. Our priority is therefore to reach as many individuals as possible while subjecting them to as little scrutiny as possible. Therefore, we aim to design a data collection approach that will prioritize preserving participant confidentiality. Our approach will be iterative pilot tests of data collection methods including embedding unique QR codes linked to surveys in firearm safety brochures and study poster signage. We will offer the opportunity for individuals to take home a cable lock after their visit or to scan the QR code on the brochure/poster to fill out the study survey and get a safety

device shipped to their address. Participants who fill out the study survey will be randomized to receive either a cable lock as the default or a choice between cable lock and lock box to test acceptance and usage rates. For those who accepted a cable lock at the hospital will automatically be grouped in the cable lock default group. The hypothesis we are testing is if iterative pilot testing will reveal a feasible method that balances pragmatism and confidentiality as well as compare acceptance and usage rates among cable locks and lock boxes.

The intended outcome of this study is development of critical evidence to facilitate the scaling of this program to our hospitals and launch a promising research program to study the acceptability, long term use, and cost-effectiveness of a scalable approach to promote safe firearm storage.

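### Follow-up is timed from enrolment and asks about storage since the visit, so people whose device is shipped are assessed after less time with it, and no item records receipt

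*Protocol*

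**What the plan says.** **Timing.** Protocol section 8.2 (Follow-up Survey) states that people who complete the initial survey and give contact details "will be contacted via text message 1 month after enrollment for a follow-up survey". There is no separate timing for shipped devices. Enrolment is not defined further; I take it as completion of the initial survey.

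**Devices handed over.** The Abstract says that "security guards offer a cable lock and safety brochure when the gun owner returns to retrieve their firearm at the conclusion of their visit". The brochure survey in 8.2 accordingly asks "Did you get a cable lock today".

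**Devices shipped.** The poster survey asks "Are you interested in receiving a firearm storage device shipped to your address", takes an address from those who say yes, and then asks "Once you receive your cable lock, how likely are you to use it in the next week". Receipt lies in the future when that survey is answered.

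**Who is followed up.** Section 5.5 admits those who took a cable lock according to the brochure survey, or who answered "yes to receiving a firearm storage device shipped to their address from the poster survey". The sentence in 8.2 that introduces the follow-up questions is narrower and names only people who accepted a cable lock.

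**What is asked.** Follow-up item 1 asks how the firearm has been stored since the visit. Item 2 is a Yes/No question: "Have you used the firearm storage device from Penn Medicine to secure your firearm". Item 3 is a write-in on other changes.

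**Allocation.** The Detailed Description for ClinicalTrials.gov, at the end of the protocol, lets people who scan either the brochure or the poster code have a device shipped. It randomises survey completers to a default cable lock or to a choice of cable lock or lock box, with usage to be compared, and adds: "For those who accepted a cable lock at the hospital will automatically be grouped in the cable lock default group".

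**The concern.** The time origin for follow-up is the same for two groups who obtain the device at different times. For a lock handed over, one month after enrolment is at least one month of possible use. For a shipped device it is one month less processing and delivery. The two follow-up questions that bear on the device inherit this difference. Item 2 counts ever-use over unequal periods, and item 1 covers, for shipped participants, days on which they could not have used the device.

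Nor can the data be repaired afterwards. Without a receipt item or a dispatch date, a No from someone who never received the device looks the same as a No from someone who received it and left it unused. Storage behaviour is a named secondary outcome (section 3.2), usage is the Aim 3 question, and shipping is one of the distribution routes whose feasibility the study sets out to examine. The error runs against shipping.

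**Working it through.** The protocol gives no shipping time, expected use rate or sample size, so there is no figure of its own to reproduce.

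**Step 1: direction, from the text alone.** Let L be the days from enrolment to receipt, and take one month as 30 days. Time with the device at the follow-up text is at least 30 days if handed over and 30 − L days if shipped. For any L above zero, the shipped group has less. Likewise L of the 30 days since enrolment, all within item 1's recall window, fall before the device arrived, whatever the pattern of use.

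**Step 2: size by route, under assumptions.** L, the 30-day use probability U, and the pattern of first use are all assumed. True behaviour is set equal in the two groups.

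- Constant rate of first use: reported use among shipped = 1 − (1 − U)^((30 − L)/30).
- Early first use: reported use after t days = 0.5 × (1 − exp(−t/5)), that is, a mean of 5 days to first use and a ceiling of 50%. At t = 30 this is 49.9%.

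Cells show reported use among shipped recipients, with the shortfall in percentage points against devices handed over.

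| Lag L (days) | Days with device | Share of 30 days lost | Constant, U = 30% | Constant, U = 50% | Constant, U = 70% | Early use |
|---|---|---|---|---|---|---|
| 3 | 27 | 10% | 27.5% (2.5) | 46.4% (3.6) | 66.2% (3.8) | 49.8% (0.1) |
| 7 | 23 | 23% | 23.9% (6.1) | 41.2% (8.8) | 60.3% (9.7) | 49.5% (0.4) |
| 14 | 16 | 47% | 17.3% (12.7) | 30.9% (19.1) | 47.4% (22.6) | 48.0% (1.9) |
| 21 | 9 | 70% | 10.1% (19.9) | 18.8% (31.2) | 30.3% (39.7) | 41.7% (8.2) |

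**Step 3: size by arm, if the same one-month follow-up is used there.** Let h be the share of the cable-lock default group that took a lock at the hospital, and let the choice group be entirely shipped. With no true effect, the difference in reported use is h × (U − use among shipped). With h = 0.5, U = 50% and a constant rate, this gives about 4, 10 and 16 points at lags of 7, 14 and 21 days. Under early use, half of 0.4, 1.9 and 8.2 gives about 0.2, 1 and 4 points. With h = 0 it is zero at every lag.

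**Step 4: after re-timing.** If the text goes out 30 days after receipt, time with the device is 30 days for shipped recipients in both arms, and the spurious difference from this source disappears for every L.

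**The case against.** Several points on the other side stand.

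- **The primary outcome is untouched.** It is the response rate. The only comparison of channels that the protocol plans is also of response rates (sections 3.3 and 5.1). A reader might infer that a planned comparison of use by channel is biased; the documents contain none. The distortion applies to pooled or descriptive use and storage results, and to any later comparison by route.
- **The likelihood-of-use item is sound.** The poster version is already tied to receipt.
- **The arm effect is conditional.** The one-month rule is in the protocol body, which is written for Aim 2. The randomisation is in the registry text, which states no follow-up interval, and the section 5.2 schedule gives Aim 3 direct and voucher distribution as well as shipping. A reader might infer that the randomised comparison is itself biased by the clock. It is not: people who are randomised and shipped alike share the same clock, unless the two device types arrive at different speeds. The imbalance arises because non-randomised hospital acceptors are put in the default group. That is a separate flaw, and re-timing the text does not cure it.
- **Still waiting at one month.** It is tempting to say that many people will be counted as non-users while the parcel is on its way. With lags of 1 to 3 weeks, nobody is. The ambiguity of a No concerns failed or very late deliveries, whose frequency the documents do not give.
- **A fixed interval from enrolment can be defended** in a pragmatic pilot, since delivery delay is part of how shipping performs. That argues for measuring the delay and reporting it, which the listed items do not allow.

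Section 8.2 also lets the investigators amend the follow-up questions. That makes the repair easy but does not correct the timing.

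**Conclusion.** The point holds, with limited scope. It follows from the protocol's text that shipped recipients are followed up after less time with the device, that item 1's window includes time before it arrived, and that item 2 cannot tell non-receipt from non-use. This can understate use and storage change for shipped devices. It reaches the cable-lock versus choice comparison only if the same follow-up interval is used there, and only to the extent that hospital acceptors sit in the default group.

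The size cannot be derived from the documents. With assumed lags of 1 to 3 weeks, it runs from under 1 point to about 30 points or more (nearly 40 at U = 70%). A claim that shipped devices will look materially worse would go beyond the evidence, because early first use combined with quick delivery makes the effect negligible. The change is still worth making, because it is cheap now and receipt dates that go unrecorded cannot be reliably recovered later.

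**What to change.** 1. Record the dispatch date of every shipped device, and open the follow-up survey with an item such as 'Have you received the device, and about when?'.
2. For any shipped device, whether requested through the poster or the brochure, send the text one month after receipt, or after dispatch plus a fixed allowance. Keep one month from the visit for devices handed over. The rule should follow how the device was obtained, not which code was scanned.
3. Word item 1 as storage since receiving the device.
4. Report item 2 among recipients, and give the proportion not received separately so that failed delivery stays visible.
5. Reconcile section 8.2 (people who accepted a cable lock) with section 5.5 (which also includes shipped devices) on who gets the follow-up.

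The cost is one extra survey item, one date field and a changed text schedule, with follow-up of shipped devices ending some weeks later. Timing from dispatch plus an allowance is simpler, but leaves a small inequality wherever delivery time differs from the allowance. The placing of hospital acceptors in the default group needs its own correction.

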5.1 Design

Aim 2 of this research study is to design and pilot test a method for collecting data on storage device use among patients and visitors who accept firearm safety materials or are interested in receiving a firearm storage device shipped to their address. The study design is an iterative pilot test of survey data collection methods and determination of scalability and feasibility for distribution of firearm storage devices. The study population and sample will be (a) individuals who are patients or visitors to PAH who are screened

for a firearm, screen positive, and accept a firearm safety brochure and storage device OR (b) individuals interested in receiving a firearm storage device and self-scan the unique QR code on the study poster in the entry hall of PAH with minimal or no security supervisor engagement. A unique QR code linking directly to the initial survey will be embedded into the firearm safety brochure as well as the poster in the entry hall of PAH next to the distribution area. Individual group (a) will be informed by security that survey participation is optional, but that it is helpful for our efforts, and that participation will be compensated with a \$10 Amazon gift card for the initial survey and a \$20 Amazon gift card for completing the follow-up survey. Individual group (b) will not be actively engaged by security, and will self-enroll in the study by viewing the posted signage and completing the QR code linked survey. Individuals who decline the device will also be eligible for the initial survey via the poster QR code, but they will not be eligible for the follow-up survey.

The primary outcome measure is survey response rate: whether an eligible visitor or patient completed the firearm storage survey after accepting firearm safety materials or after scanning the QR code on the poster. This will be measured through Qualtrics survey completion rate and PAH Evolv security system foot traffic. We will use the survey completion rate as the numerator and the number of people scanning positive for a firearm as the denominator for this rate.

The secondary outcome measures are from initial and follow-up survey responses: (1) firearm storage behavior, (2) likelihood of using cable lock within the next week (extremely unlikely to extremely likely scale). These outcomes are directly tied to questions asked in both surveys.

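### Section 8.2 puts the follow-up questions only to people who accepted a cable lock, leaving out poster participants whom 5.5 admits; poster item 7 has no gate, and the Unlocked storage option is ambiguous

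*Protocol*

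**What the plan says.** **Who is followed up.** Section 5.5 gives two routes: yes to a cable lock "in the initial brochure survey or yes to receiving a firearm storage device shipped to their address from the poster survey". The follow-up part of 8.2 describes the eligible differently: "Eligible participants from the initial survey, those who answered yes to accepting a cable lock, will be asked the following questions". The corresponding poster question (item 3) is "Are you interested in receiving a firearm storage device shipped to your address". The poster paragraph of 8.2 promises a $20 card for completing the follow-up and adds: "Only eligible participants will receive a text with a link to complete the optional follow-up survey".

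**Likelihood of use.** Brochure item 6 is conditional on a yes answer. Poster item 7 carries no condition: "Once you receive your cable lock, how likely are you to use it in the next week". Section 7 says that the shipped device may be a cable lock, a lock box or both. Sections 3.2, 5.1 and 9 name the outcome after the cable lock; the two ClinicalTrials.gov descriptions at the end of the protocol name it after a gun safety device.

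**Storage.** All three surveys offer the same four options: a locked safe or gun cabinet, a trigger or cable lock, Unlocked, and other. A bracket explains Unlocked in three phrases, about a lock, a locked container and a locked cabinet. Section 9 analyses this option as unsecured.

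**Source of the secondary outcomes.** Section 5.1 takes both from initial and follow-up responses and says: "These outcomes are directly tied to questions asked in both surveys".

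**The concern.** The secondary outcomes depend entirely on who is asked which question and how the answer options read. If the follow-up is programmed from the 8.2 phrase, poster participants are not asked about storage or device use at 1 month, and no later analysis can recover those answers. If poster item 7 is shown to everyone, the likelihood outcome pools people awaiting a device with people who declined one. If a respondent who keeps a firearm in a locked container can reasonably tick Unlocked, secondary outcome (1) records locked storage as unsecured, both at the initial survey and at follow-up.

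**Working it through.** No statistical calculation applies: the point depends on no rate, sample size or error level. The check sets the sections side by side and counts the listed items.

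**1. Follow-up eligibility**

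| Source | Brochure route | Poster route |
|---|---|---|
| 5.5 | yes to a cable lock | yes to a shipped device |
| 8.2, follow-up phrase | yes to a cable lock | none |

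That is 2 routes against 1. The seven poster items cover phone number, visit date, interest in a shipped device, reason for declining, address, usual storage and likelihood of use. Items asking whether a cable lock was accepted: 0 of 7. Read literally, the 8.2 phrase therefore excludes every poster participant.

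Another sentence in 8.2 says that initial-survey completers who give contact details will be texted at 1 month. It is already limited by "Only eligible participants will receive a text with a link to complete the optional follow-up survey" in the same section, so it is not counted as a third rule.

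**2. Poster item 7**

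Answer paths that reach it, counting each 4c choice once:

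- Yes to item 3: 1 path.
- No to item 3: 4a (already has one), 4b (prefers a different device), 4c pick-up, 4c local receipt, 4c other: 5 paths.
- Total: 1 + 5 = 6.

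On 4a and 4b nothing in the protocol puts a device on its way. On 4c the survey records only what the respondent would be open to, for example "Returning to Penn Medicine to pick up a free cable lock"; no pick-up or local delivery is arranged. A gate on yes to item 3 keeps 1 path and removes 5, and it matches the poster criterion in 5.5. These are paths, not people; the protocol gives no poster counts.

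**3. Storage option c**

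Of the three bracketed phrases, the first and third carry a negation and the middle one (locked container) does not: 2 of 3. The wording is the same in brochure item 7, poster item 6 and follow-up item 1: 3 of 3 surveys. Two readings are possible:

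- The first negation extends to the middle phrase, and a locked container is not Unlocked.
- The middle phrase stands alone, and a locked container is Unlocked.

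Options naming a lock box: 0 of 4. The surveys' own preference item lists lock box, gun safe and gun cabinet as separate devices, so option a is not a clear home for a lock box. A person using one could tick a, c or d.

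**4. Likelihood of use at follow-up**

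The listed follow-up items are storage since the visit, device used, and other changes. Items on the likelihood scale: 0 of 3. The nearest is item 2, "Have you used the firearm storage device from Penn Medicine to secure your firearm", a yes/no record of actual use.

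**The case against.** **The poster exclusion rests on one phrase.** Section 5.5 is the eligibility section and admits the poster route, 8.2 offers poster participants the follow-up card, and follow-up item 2 is neutral as to device. This stands. A reader might infer that the protocol plans to leave poster participants out, or that their data will certainly be lost. The documents do not support that; they support a conflict that loses the data only if the 8.2 phrase is what gets programmed.

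**The 4c respondents.** A reader might infer that people who choose pick-up or local receipt under 4c also expect a device, so that filtering item 7 on item 3 would discard valid answers. The documents do not support this. Being open to an arrangement is not having one, and 5.5 does not admit these people to follow-up.

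**Likelihood in both surveys.** The 5.1 sentence can be read loosely, with actual use counting as tied to likelihood of use. The follow-up is also described as adding questions, and the investigators may amend it. This reduces the point to a clarification. It does not remove it, because the list repeats the storage question and not the likelihood question.

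**Lock boxes.** The 5.2 timetable puts Aim 2 data collection in months 2 to 6 and lock-box distribution, under Aim 3, in months 9 and 10. Few lock boxes, if any, would be shipped during Aim 2, so the misfit of the item 7 wording is limited. The storage question is affected less by this argument, since it asks about usual storage, including containers people already own.

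**Option c.** The heading Unlocked and the section 9 label make the intent fairly clear, and an other option exists. That makes misclassification less likely but not impossible.

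**Permission to refine the surveys.** It makes the correction cheap. It does not reconcile the text.

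**Conclusion.** The point holds as an internal inconsistency and two item defects, all bearing on the secondary outcomes:

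1. Sections 5.5 and 8.2 disagree on follow-up eligibility (2 routes against 1). The literal 8.2 phrase would leave poster participants' 1-month storage and use answers uncollected.
2. Poster item 7 lacks the gate that brochure item 6 has, so answers from people who declined a shipped device mix into secondary outcome (2).
3. Option c allows locked-container storage to be recorded as unsecured, in all three surveys.
4. Minor: no listed follow-up item uses the likelihood scale that 5.1 attributes to both surveys.

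Item 1 assumes that the follow-up is built from the 8.2 phrase. Items 2 and 3 assume that the surveys run as listed. A reader might also infer a known bias or a threat to the main result. Neither follows: the primary outcome, the survey response rate, is not affected, and the documents give no counts from which a size or direction of bias could be derived.

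**What to change.** - **8.2, follow-up:** replace the phrase with the two-route rule of 5.5.
- **Poster item 7:** ask it only after yes to item 3, and say *your device*. Filter data already collected in the same way. If respondents who chose pick-up or local receipt under 4c are asked, report them separately.
- **Storage options:** reword option c as *not locked, and not in a locked container, safe or cabinet*, and name a locked container or lock box in one of the locked options. Use identical wording in all three surveys and in section 9.
- **3.2 and 5.1:** state that likelihood of use is measured at the initial survey and that actual use (follow-up item 2) is the follow-up measure.
- **Outcome name:** reconcile the cable-lock wording of 3.2, 5.1 and 9 with the gun-safety-device wording of the ClinicalTrials.gov descriptions. The latter cover Aims 2 and 3 and the protocol body covers Aim 2 only, so the investigators should say which scope is meant.

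The cost is a few text and branching edits, within the protocol's own allowance to refine the surveys. The downside is that answers before and after the change are not fully comparable, so the survey version should be recorded with each response and results reported by version.
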